The overall Specific Aim of this proposal is to determine the effect of opioid taper on pain sensitivity in patients with chronic pain. Specifically, in a well-characterized sample of men and women with chronic neuropathic pain and receiving high-dose opioid therapy (200mg morphine equivalents/day [MED]), experimental pain responses will be serially described over the course of an individualized opioid taper to a safer dose of 90mg MED for up to 12 months. Changes will be inspected within-subject over time, and pain perception will be measured with two valid and reliable experimental pain induction techniques commonly used to measure OIH (cold-pressor, quantitative sensory testing); in addition, related functional improvements and subject-level predictors of response will be described. Hypothesis 1. Subjects undergoing opioid taper will have improved pain responses over time compared to within-subject baseline as measured by cold-pressor and quantitative sensory pain testing. Hypothesis 2. Improvements in experimental pain responses will be positively related to improved functional outcomes compared to within-subject baseline as measured by the PROMIS physical, mental and social health measures. Hypothesis 3. Degree of improvement in experimental pain responses related to opioid taper will be predicted by demographic, pain, and opioid use history characteristics of the subject. Data showing that pain perception improves as opioids are withdrawn would provide an evidence-based, mechanistic rationale for opioid taper in patients with chronic pain and have the potential to support a sea-change in opioid prescription practices. In that ongoing opioid therapy brings with it significant health risks for the patient and the community, it is critical that empirical evidence of its efficacy be demonstrated to balance the benefits with the risks of adverse events, potential misuse and abuse, and patient safety.

Primary outcome variable(s)

The primary dependent variable, pain perception, will be measured using two highly reliable and valid pain induction techniques, the cold-pressor test (CPT) and quantitative sensory testing (QST), employing procedures consistent with those described in the literature. Order of pain testing will vary, and three aspects of the pain response will be captured at each study session: evoked pain; temporal summation; and conditioned pain modulation, which map on to the hypothesized peripheral, spinal and supra-spinal mechanisms of OIH.

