
Study Design

Phase*

Not applicable

Design

A prospective time-series survey design will be utilized to measure the experimental (CPT and QST) pain responses of chronic pain patients on high-dose opioid therapy (200mg MED) prior to and then regularly during and following a voluntary opioid taper. Data will be collected weekly during the active taper period; once the subject has reached a stable maintenance dose (90 MED), assessments will occur monthly until month 12. Because our previous work has shown stability in pain responses in patients on

high-dose opioid therapy over time (6 months), and the clinical imperative of tapering patients to safer doses, a control group of patients maintained on high-dose therapy is not included. Consistent with expert opinion in the field, a longitudinal within-subject design is planned.

Study duration

The overall duration of the study is two years, during which time all subjects will be enrolled and complete the study. Data will be collected weekly during the active taper period; once the subject has reached a stable maintenance dose (less than or equal to 90 MED), assessments will occur monthly until month 12. If funded, the study would begin Oct 1, 2018.

Resources necessary for human research protection

Describe research staff and justify that the staff are adequate in number and qualifications to conduct the research. Describe how you will ensure that all staff assisting with the research are adequately informed about the protocol and their research related duties. Please allow adequate time for the researchers to conduct and complete the research. Please confirm that there are adequate facilities for the research.

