Participants will be recruited from those treated at the large and nationally-renowned Penn Pain Medicine Center at the University of Pennsylvania Penn Medicine Neuroscience Center. The Penn Pain Medicine Center provides interdisciplinary, multimodal pain care to over 12,000 outpatients annually, an estimated 20% of whom are taking opioids on a regular basis. At any one point in time an estimated 50 patients are undergoing opioid taper, up to half of whom are tapered from opioid doses greater or equal to 200mg MED. Due to anticipated rates of dropout, 25% oversampling for these individuals is planned. Results from previous studies have demonstrated moderate to large effect size estimates of opioids on cold-pressor and QST experimental pain responses. Based on these estimates, a sample size

of 25 will have over 99% power to detect differences in outcome. Using an alpha of 0.05/4 (Bonferroni correction) to account for multiple outcomes, we will have over 90% power to detect significant changes at the 0.01 level for all of the outcomes. Cross-sectional and prospective studies demonstrate statistically significant differences in experimental pain responses with changes between 80-90mg MED (10,11,70); since MED decreases in the proposed work will be 110 MED (tapers from 200MED to 90MED), we anticipate having no difficulty discerning taper effects on pain responses.

Key inclusion criteria

(1) between ages of 21-60; (2) documented chronic neuropathic non-malignant pain condition of at least one year duration; (3) on 200mg MED for at least 6 months; (4) have fully engaged in all prescribed non-opioid pain management treatments; (5) willing to undergo prescribed opioid taper; (6) otherwise in good physical and mental health, or in the care of a physician who is willing to take responsibility for such treatment; and (7) able to understand the purpose and instructions of the study, and provide informed consent as approved by the University of Pennsylvania IRB.

Key exclusion criteria

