as a biological variable will be considered in all analyses. Statistical Analyses. The effect of opioid taper on changes in pain responses (CPT, QST), and functional outcomes (PROMIS domains) over time will be examined using longitudinal mixed-effects regression modeling, using general linear regression modeling with regularization as a function of baseline dose, end dose, and taper rate. These longitudinal profiles will be examined using a linear mixed effects framework with SAS Proc Mixed in which all available data collected during follow-up are used. Mixed models can account for the correlation between repeated measures and handle non-excessive missing data better than traditional models and allow for use of time-independent and time-dependent covariates. To assess patterns of attrition over time, a comparison of withdrawal rates and time to withdrawal will be included. Separate mixed effects regression models will be generated for each of the continuous outcome measures of interest (pain responses, functional outcomes). Random slopes and intercepts will be modeled to represent the participant-level deviation from the fixed-effect slope over time and intercept, respectively. Restricted maximum likelihood estimation will be used and the most appropriate covariance structure examined. Scores will be analyzed as repeated observations of the dependent variable, with mean-centered baseline outcome scores serving as a covariate. Other predictor variables will include baseline demographic characteristics of the patient, severity and chronicity of pain suffered, and opioid use history. Baseline measures will be analyzed as time-independent covariates. The Akaike information criterion will be used to evaluate overall model fit and to select the best-fitting longitudinal change pattern. .

The following documents are currently attached to this item:

There are no documents attached for this item.

Data confidentiality

- x Paper-based records will be kept in a secure location and only be accessible to personnel involved in the study.**
- x Computer-based files will only be made available to personnel involved in the study through the use of access privileges and passwords.**
- x Prior to access to any study-related information, personnel will be required to sign statements agreeing to protect the security and confidentiality of identifiable information.**
- x Wherever feasible, identifiers will be removed from study-related information.**

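### AIC chooses the time pattern for each pain outcome and no other test of Hypothesis 1 is named, so the stated alpha is not assured

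*Combined protocol and SAP*

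**What the plan says.** Objectives (Overall objectives) gives Hypothesis 1 as: "Subjects undergoing opioid taper will have improved pain responses over time compared to within-subject baseline". Study Design (Design) states that "a control group of patients maintained on high-dose therapy is not included", so the evidence for Hypothesis 1 is the course of each outcome over time within subjects.

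Analysis Plan (Statistical Analyses) fits a separate mixed model to each outcome, with random intercepts and slopes and REML estimation. One sentence leaves the covariance structure open for examination. The closing sentence then gives AIC a different job: "The Akaike information criterion will be used to evaluate overall model fit and to select the best-fitting longitudinal change pattern". The plan lists no candidate patterns, names no coefficient or contrast for Hypothesis 1, and makes no allowance for the selection.

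Accrual is the only place that states a significance level: "Using an alpha of 0.05/4 (Bonferroni correction) to account for multiple outcomes". The same sentence goes on to claim "over 90% power to detect significant changes at the 0.01 level for all of the outcomes".

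**The concern.** With no comparison group and no named contrast, the natural test of Hypothesis 1 is the test of the time terms in the model that AIC has picked. AIC picks the pattern that follows the observed data best for its number of terms, and under no true change that includes chance fluctuation. A p-value computed as though the pattern had been set beforehand ignores this search and is generally too small.

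What is at stake is the error control that Accrual claims. The selection is repeated for each outcome, so any excess enters every member of the Bonferroni family. Different outcomes may also end with different patterns. That is not wrong in itself, but without a named quantity per outcome the reader cannot say what improvement over time was tested in each case.

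**Working it through.** **Inputs from the documents.** N = 25; weekly visits in the taper, then monthly to month 12 (Design); 30 to 40 visits expected (Subject compensation); taper from 200 to 90 mg MED (Accrual) at an average of 10-15% per month (Procedures); alpha 0.05/4 (Accrual). **Not in the documents:** candidate patterns, variance components, sidedness, the test itself. These are assumed below.

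**1. The plan's own figures.** 0.05/4 = 0.0125, not 0.01. Over four independent outcomes the family rate is 1 − (1 − 0.0125)^4 = 0.049, or 1 − (1 − 0.01)^4 = 0.039 at 0.01. The power claims cannot be reproduced, because the effect is given only in words ("moderate to large effect size estimates of opioids on cold-pressor and QST experimental pain responses"). The documents state no error rate for the selection step.

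**2. Smallest case by hand: linear against quadratic.** In large samples with no true change, let Z1 and Z2 be independent chi-square(1) statistics for the linear term and the added term. AIC keeps the quadratic when Z2 > 2, which has probability 0.157. Critical values at 0.0125 are 6.239 (1 df) and −2 ln(0.0125) = 8.764 (2 df).

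Rejection rate = P(Z2 ≤ 2) × 0.0125 + P(Z2 > 2 and Z1 + Z2 > 8.764) = 0.843 × 0.0125 + 0.0089 = 0.0194 (second term by numerical integration).

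0.0194/0.0125 = 1.56 times nominal.

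**3. Simulation under no mean change.** 25 subjects; 33 visits (baseline, 26 weekly, 6 monthly; within the expected 30 to 40); intercept SD 1, residual SD 1, random-slope SD 0 to 4 per year; complete normal data. Each shape was fitted by ML, the lowest AIC kept, and its time terms tested jointly at 0.0125. There were 60,000 trials per setting (Monte Carlo error about 0.04 on a ratio).

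A one-term shape fixed in advance rejected at 0.012 to 0.013, a ratio of about 1.0. After AIC selection, the ratio to nominal was:

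| Candidate set | Random effect on first time term only | Random effects on all time terms |
|---|---|---|
| Linear, quadratic | 1.18-1.29 | 1.42-1.50 |
| Linear, quadratic, piecewise | 1.25-1.38 | 1.52-1.61 |
| Linear, quadratic, cubic | 1.32-1.43 | 1.63-1.73 |
| Three one-term shapes | 0.97-1.75 | 0.98-1.67 |
| Linear, log, quadratic, piecewise | 1.25-1.76 | 1.56-1.95 |
| Seven shapes | 1.38-2.06 | 1.76-2.27 |

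The first column runs slightly low, because the multi-term tests there are conservative by themselves (0.006 to 0.009 when prespecified). The linear/quadratic row in the second column is close to the hand result.

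**4. Family rate over four independent outcomes, 1 − (1 − p)^4.** p = 0.0154 gives 0.060; p = 0.019 gives 0.074; p = 0.025 (exact doubling) gives 0.096.

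**5. A rougher cross-check.** Taper lengths varied from 3.7 months (55%/15%) to 7.6 months (ln 0.45/ln 0.90), N = 20 or 25, covariance treated as known, 3,000 trials per setting. At 0.0125, fixed linear rejected 1.0-1.5%, linear/quadratic 1.7-2.4%, three to four shapes 2.1-3.3% and six shapes 2.8-3.9% (standard error 0.2-0.35 points). A further run of this setup put three to four shapes at about 1.6 to 2.2 times the fixed-linear rate. The direction agrees with step 3. The larger six-shape figures show that 2.3 is not a ceiling.

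**The case against.** The strongest reply is that the plan never says the selected pattern's p-value will be read as the test of Hypothesis 1. It mentions a fixed-effect slope, and it models outcomes against baseline dose, end dose and taper rate; either might carry the inference while AIC only describes shape. If so, this inflation would not arise. That is why the point is conditional. It does not remove the point: dose and taper-rate terms explain how subjects differ, not whether the mean has moved from baseline, and the slope is mentioned only to define the random effects. Nor can the AIC sentence be read as covariance choice, since the covariance structure has its own sentence and the AIC sentence names the change pattern.

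Other objections stand and limit the claim:

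- Hypothesis 1 is directional, while the simulated event is any rejection of no change, including worsening. The rates are not rates of falsely concluding improvement.
- The simulations omit the baseline-score covariate that the plan specifies. The shortest taper in step 5 gives only about 25 visits, below the 30 expected.
- The Bonferroni level appears only in the power paragraph of Accrual; the Analysis Plan does not adopt it. The study calls itself an observational pilot.
- Objectives links the three pain aspects to different mechanisms, so different trajectories are plausible. Requiring one common shape for every outcome would be a preference, not a correction.

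**Conclusion.** The point holds in conditional form. The plan lets the data choose the time pattern and offers no other test of Hypothesis 1. Testing the chosen terms as though prespecified generally raises the false-positive rate, by an amount the plan leaves undetermined. At 0.0125 the main simulation gives roughly 1.0 to 2.3 times nominal: about 1.2 to 1.7 for a short polynomial list, approaching or passing 2 only at the upper end with four or more shapes, and about 1.0 for one-term shapes with large slope variation. These figures rest on assumed candidate sets, variances, complete data and a joint two-sided test.

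A reader might infer that the rate is simply twice the stated alpha. The documents do not support a single multiplier, and the stated alpha is itself given two ways. A reader might also note that ratios of 4.2 to 4.5 appear when subjects differ in curvature but only the linear slope is random. A prespecified quadratic already gives 3.7 there, so that is mainly misspecified random effects and not AIC selection.

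**What to change.** Before data are examined, state in the Analysis Plan:

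- one Hypothesis 1 quantity for each pain outcome from a fixed time model, for example the linear slope the plan already mentions, or the model-estimated change from baseline to month 12, with random effects that match the fixed time terms;
- one alpha for these tests (0.0125 or 0.01, not both), and whether they are one- or two-sided;
- that AIC is limited to the covariance structure and to descriptive or sensitivity shapes, with ML rather than REML wherever models with different fixed time terms are compared.

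If AIC shape selection is to stay in the Hypothesis 1 test, repeat the whole selection inside a subject-level bootstrap or permutation and take the p-value from that.

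The cost is a few sentences and no new data. The drawback is some loss of power if the fixed shape fits less well than a selected one would.
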